**Assessment of Intervention Adoption: In-Person Observation**  
*(Select Nurses and Staff: observation of workflow and communication techniques)*

The in-person observation of intervention adoption involves commonly occurring procedures within a medical setting, including the ongoing documentation and review of daily workflow and communication procedures.

We are therefore seeking a *waiver of documentation of consent and a waiver of HIPAA authorization* for the in-person observation portion of the study. More specifically, we are requesting this waiver because: **a)** the observation portion of the study is no greater than minimal risk, **b)** the purpose of the observation will be clearly outlined for nurses and staff in the Information Sheet (see “*InformationSheetInPersonObs...*” document) e-mailed to them prior to the scheduled observation, **c)** ample time will be given to each nurse/staff to review the Information Sheet in full and ask questions of study staff regarding the observation, and **d)** PHI will not be reused or disclosed to any other person or entity except (i) as required by law, (ii) for authorized oversight of the research study, or (iii) for other research for which the use or disclosure of PHI would be permitted by the HIPAA Privacy Rule.

Prior to in-person observation, the study coordinator will contact each site’s vaccine champion to determine 1-2 days that would be optimal for study staff to be onsite. Once the observation schedule has been determined, all nurses and staff who are scheduled to work on the specified day(s) will be e-mailed an Information Sheet (see “*InformationSheetInPersonObs...*” document) by the study coordinator, which they may review at their own pace prior to the observation date. They may e-mail the project coordinator with any questions, or bring questions to the attention of the study staff on the scheduled visit day prior to the start of any observation. The content of the Information Sheet will be reviewed again by study staff with practice nurses/staff on the visit day prior to the start of any documented observation (any nurses/staff not previously known to be working that day will be given a hard copy of the Information Sheet upon arrival by the study staff and given ample time to review).

As stated previously, although study staff will observe OB/GYN practice nurses and staff during patient encounters, practice patients will NOT be the target of the observation, and no patient information (in either individual or aggregate form) will be collected. Rather, the focus of observation will be the select practice personnel only. Information recorded during the observation session will be

written in a generic manner such that specific nurses/staff/patients will not be identifiable. Notes will describe the general workflow processes and communication methods used, rather than specific unique behaviors or exact dialogue. For example, study staff may document “*...when patient declined to receive the Tdap vaccine, the practice nurse gave them an informational handout and told them the doctor may speak with them further.*” The study staff will only observe the initial nurse/staff interaction with the patient, and will not continue to observe once the provider (doctor or midwife) enters for the visit. Although the patient is not the study subject, prior to each observation, study staff will explain to the patient in simple language the purpose of the observation (i.e., to take notes regarding the nurse/staff work routine), and any patient that communicates discomfort or preference to not be observed, will not be observed.

### Provider & Nurse Survey and Culture Survey Dissemination

We are seeking a *waiver of documentation of consent and a waiver of HIPAA authorization* for the Provider & Nurse Survey and Culture Survey portion of the study. We are doing so because: **a)** the surveys are no greater than minimal risk (a brief online survey with unobtrusive questions), **b)** a detailed Information Sheet (see “*InformationSheetProviderNurseSurvey...*” and “*InformationSheetPracticeCultureSurvey...*” documents) will be made available to each subject prior to the start of the survey, **c)** ample time will be given to each subject to consider participation (subjects are notified of the survey via e-mail and can review the information sheet and/or ask questions of study staff for as long as necessary before deciding about survey completion), **d)** no identifiers will be included on the survey form (only subject IDs), and the separate document linking subject name to subject ID will only be made available to a limited number of study staff, will be kept under double-locked conditions, and will be destroyed three years after study completion, and **e)** PHI will not be reused or disclosed to any other person or entity except (i) as required by law, (ii) for authorized oversight of the research study, or (iii) for other research for which the use or disclosure of PHI would be permitted by the HIPAA Privacy Rule.

### Patient (EHR) Level

**EHR Data Extraction:** We are seeking a *waiver of consent and a waiver of HIPAA authorization* for the EHR data extraction portion of the study. We are doing so because: **a)** we believe that this research cannot be practicably conducted without such a waiver, as we cannot feasibly obtain consent and HIPAA authorization from all potential subjects (10,000+ in total subject pool), **b)** site liaisons and report builders have routine access to patient records, **c)** a minimal number of patient-level data fields will be extracted from the EHR (just enough to complete analysis) **d)** a plan to protect EHR data during all data transfers will be implemented (see “Privacy & Confidentiality” section for details), **e)** any individual-level data will be destroyed three years after study completion, and **f)** PHI will not be reused or disclosed to any other person or entity except (i) as required by law, (ii)

for authorized oversight of the research study, or (iii) for other research for which the use or disclosure of PHI would be permitted by the HIPAA Privacy Rule.

## 8. AUDIO/VIDEO RECORDINGS

All site meetings (both virtual and in-person) held during the training phase may be audio and/or video recorded using a laptop or handheld recording device (in-person meetings) or via the Zoom recording option (virtual meetings) (see “Privacy and Confidentiality” section for more detail). These archived audio/video files will allow for the review of meeting content by site personnel who were unable to attend the meeting live, or by those who simply wish to review the meeting discussion for a second time.

The archived site meeting audio/video files will be stored on a secure Box platform, accessible only to study staff and site personnel from the corresponding practice site (each site will have their own Box folder ensuring meetings from other sites are not viewable to outside personnel). Invites to the secure Box folder will be e-mailed from study coordinators directly to site personnel. As soon as the video files have been uploaded to the secure Box platform, they will be deleted from the laptop or handheld recording device. Once the study has been fully completed, all video files will be deleted from the shared Box folder.

## 9. RISKS TO SUBJECTS

**Practice Level Risk:** This project involves QI trainings/interventions which aim to improve upon the existing communication techniques and workflow procedures at each intervention practice site. Planned study trainings/interventions are widely accepted among medical practices (e.g., practice providers/nurses/staff attending an informational meeting regarding the risk of influenza in the pregnant population), and do not involve any novel high-risk changes to practice structure or procedures. Practice sites in the control group will continue to utilize “best-practice” guidelines. Thus, at the practice level, anticipated overall study risk is very low.

**Site Personnel & Patient Level Risk:** The primary risk to site personnel and practice patients is the risk of a breach of confidentiality, though overall risk remains low.

To reduce risk, personal information being collected from site personnel or practice patients (EHR data) has been minimized, and when possible is being collected in aggregate form.

A number of policies, procedures, and technical safeguards (described in the “Privacy & Confidentiality” section of this protocol) will be in place to ensure that there is no breach of confidentiality as a result of this study.

## **10. POTENTIAL BENEFITS TO SUBJECTS**

Practice personnel will receive targeted training related to: influenza and pertussis disease as it pertains to the pregnant population, communication, and optimization of office workflow as it relates to the improvement of immunization rates within their practice. As such, practice personnel who participate in both the training and ongoing QI portions of the study will have the opportunity to apply for MOC, CME, or CNE credit.

There are no anticipated benefits for practice patients beyond those inherent to the overarching study goals (i.e., an improvement in flu and Tdap immunization rates).

## **11. COSTS FOR PARTICIPATION**

There will be no costs incurred by participants.

## **12. PAYMENT FOR PARTICIPATION**

For completing each “PDSA Cycle” survey and “Practice Time & Cost” survey, each vaccine champion will receive \$5. Payment will be in the form of a gift card or check, and will be mailed to the vaccine champion at the conclusion of the 12 month intervention phase. Payment made will be the cumulative total of all completed monthly surveys (12 PDSA surveys + 12 Time & Cost surveys = 24 total surveys), for a maximum payout of \$120 (24 surveys x \$5 = \$120). Additionally, if manual chart review is necessary for any NY practice sites, each vaccine champion will receive \$20 for each monthly review. As with the above listed surveys, payment will be in the form of a gift card or check, and will be mailed as a cumulative payment to the vaccine champion at the conclusion of the 12 month intervention phase. To receive payment, subjects will enter their home address information into a secure REDCap field at the conclusion of the last online survey. This address information will be accessible only by study staff, and will be deleted as soon as the payment has been mailed.

For completing the “Provider & Nurse Survey” portion of the study, each subject will receive \$40. For completing the “Practice Culture Survey” portion of the study, each subject will receive \$10. For both surveys, payment will be in the form of a gift card or check, and will be mailed or e-mailed to the subject within 6 weeks of survey completion. Subjects will enter their home address and e-mail information into a secure REDCap field at the beginning of each online survey. This information will be accessible only by study staff, and will be deleted as soon as the payment has been sent.

Additionally, subjects completing the above surveys will be entered into a drawing for a \$75 gift card for each survey completed. Health systems will have the ability to opt out of this additional drawing incentive if it conflicts with their institutional policy. Disclosure of the approximate chances of winning, and when required per institutional policy, procedures for the inclusion of those who do not wish to complete the survey will be included in the survey invite e-mail and Information Sheets. Winners will be chosen at random using a secure computer-generated randomization program containing the names of all participating subjects. Winners will be notified within 48 hours of being selected. Payment will be sent to the winners using the contact information collected in the address/e-mail field of their REDCap survey.

For serving as an intervention site, a single practice-level payment will be offered in the amount of \$250. This payment will be in the form of a gift card or check, and will be disseminated to the vaccine champion from each intervention location. Payment may be used for any practice-wide item(s) deemed beneficial by the vaccine champion. If manual chart review is necessary at a practice site (and thus additional payment to the vaccine champion is made), the \$250 practice-level payment for that site will be reduced by the total payout amount for the manual chart review.

### **13. SUBJECT WITHDRAWALS**

During aim/phase 1 of this study (August 2019-July 2020) all health systems and affiliated practice sites agreed to participate in this quality improvement effort. While we do not anticipate a high level of subject/site withdrawals, any site wishing to end their involvement in the quality improvement initiative may do so at any time. Any practice personnel wishing to abstain from participation in quality improvement activities (trainings, ongoing meetings, adoption of new workflow procedures) are free to do so. Any vaccine champion who does not fully complete all monthly study activities during the 12 month intervention period, will still receive payment for all completed surveys prior to their withdrawal. All subjects (practice personnel) are free to discontinue participation at any time, without consequence.

### **14. PRIVACY AND CONFIDENTIALITY OF SUBJECTS AND RESEARCH DATA**

The following data collection and storage procedures will be implemented at each study site, to ensure that subject privacy and confidentiality are maintained throughout the entirety of the research process:

**Data obtained via e-mail and REDCap during the training phase:**  
*(Site personnel names collected during the e-learning modules and site meetings)*

Study coordinators will maintain a list of site personnel who have successfully completed their e-learning modules and who attended follow-up site meetings. These names will be obtained via e-mails from the vaccine champions and/or REDCap surveys. The lists will be stored in password protected Excel/Word files on a password protected computer for the purposes of confirming requests for MOC, CME and CNE credit. No additional study information (e.g., future survey responses) will be contained within this file. All files will be stored on a secure server within each university system (URMC/UCLA). These individual-level training completion files will be deleted once they are no longer necessary (i.e., once all credit applications are in). Only aggregate data, not individual names, will be stored long-term by study staff regarding the completion of online training content by site personnel (i.e., the total number of providers, nurses, and staff who did/didn't complete the training).

**Data Obtained via REDCap during the intervention adoption & assessment phase:**  
*(PDSA cycles, Time & Cost Surveys, Provider & Nurse Survey, Practice Culture Survey)*

For study measures completed via a REDCap survey, all subject names and corresponding e-mail addresses will first be collected by the study coordinators from either the previously

identified health system liaisons ([name] for URMC, [name] for RRH, [REDACTED] or the assigned vaccine champions (not yet determined) for each site. The names, e-mail addresses, site locations, and an assigned subject ID for each person, will be stored in a password protected Excel/Word file on a password protected computer. No additional study information (e.g., survey responses) will be contained within this file. All files will be stored on a secure server within each university system (URMC/UCLA).

Once e-mail addresses have been obtained, each study coordinator will upload the e-mail addresses onto the secure REDCap platform. Surveys will automatically be disseminated to the appropriate subjects in the appropriate timeframe (weekly, monthly, bi-monthly) through previous REDCap programming completed by the study coordinator. Completed REDCap survey data will be exported in an Excel/Word file and stored under double-locked conditions on a secure server within each university system (URMC/UCLA), before transfer to the [REDACTED] Health Sciences Box platform (a regulated platform frequently used by [REDACTED] for data storage and transfer online) for analysis by the project's [REDACTED] data specialists.

Surveys for which payment (gift card or check) is given will request home address information within the survey questionnaire. This information will temporarily remain on the secure REDCap platform and/or secure university server, and will be utilized by the study coordinators during the payment mailing process. All personal address information will be destroyed once payments for phase 2 have been fully completed.

#### **Data Obtained via EHRs:**

EHR data reports will be generated only by the specified EHR report builder for each health system. A minimal number of patient-level data fields (only those needed for analysis) will be extracted from the EHRs. For data verification purposes, identified study staff will check a small percentage of patient eRecord files to ensure the accuracy of generated EHR reports. The identified individuals will have access to EHR files and will complete all appropriate eRecord training prior to conducting data verification. All individual level data will be stored in encrypted form on the secure Box platform. Whenever possible, data will be stored in aggregate form. "Rate Feedback" reports received by site personnel will present immunization rate information in aggregate form only (no individual patient information), and the recipient of the report will be identified by a study ID# rather than a name.

**All Research Data:** All individual-level research data (saved in encrypted form) will be stored on the secure [REDACTED] Health Sciences Box platform (a regulated platform frequently used by [REDACTED] for data storage and transfer online). Aggregate data will be stored on secure university servers and/or the secure Health Sciences Box platform. Analyzed data reports from the [REDACTED] data specialist will be sent in a de-identified form via secure e-mail to the project PI for review. Any files linking subject name to subject ID# (e.g., REDCap survey files, personnel ID files for feedback reports) will be password protected and stored on secure university server systems accessible only by study staff.

## 15. DATA / SAMPLE STORAGE FOR FUTURE USE

**Hard copy data:** Due to the online (e.g., REDCap) nature of data collection during phase 2 of the study, no hard-copy documents will be created or stored.

### Electronic data:

#### *Site Meeting Attendance:*

Files containing site meeting attendance records will be stored in password protected Excel/Word files on password protected computers. No additional study information (e.g., survey responses) will be contained within these files. All files will be stored on a secure server within each university system (URMC/UCLA). Once all MOC, CME and CNE credit requests have been completed, attendance records will be destroyed.

#### *E-learning modules, PDSA cycles, Time & Cost Surveys, Provider & Nurse Survey, Practice Culture Survey:*

Survey data is stored immediately upon completion by the REDCap website. Study staff will then access the secure password-protected survey site to generate data reports when needed. These data reports will be stored on password-protected computers within the locked offices of study staff (double-locked conditions) using the secure university servers. Any *personal address information* obtained from study subjects for the purposes of payment will be destroyed once payments for phase 2 have been fully completed.

As we are seeking a waiver of documentation of consent and a waiver of HIPAA authorization for the survey portions of the study, there will be no need to store consent forms with subject names.

#### *EHR data output:*

Individual-level EHR data reports (saved in encrypted form) and aggregate EHR data reports will be stored on the secure UCLA Health Sciences Box platform (a regulated platform frequently used by UCLA for data storage and transfer online). Analyzed data reports from the UCLA data specialist will be sent in a de-identified form via secure e-mail to the project PI for review. All data will be stored 3 years beyond study completion.

## 16. DATA AND SAFETY MONITORING PLAN

This study presents no more than minimal risk, however there is still a risk to privacy and confidentiality. Prior to the start of aim/phase 1, the research team from both NY and CA met to create a data safety monitoring plan. PIs, team members, and representatives from each study clinic regularly discuss communication and action plans in the unlikely event that an adverse event occurs. Information on how to contact the study team via phone, mail or email is readily apparent to all participating providers and care team members. Though adverse events are not anticipated, should any occur they will be reported to the site PI (“team leader”) in each state and then to the IRB at the time of the event, and copies of all correspondence regarding the event with the IRB will be shared with the CDC, as needed.

## 17. DATA ANALYSIS PLAN

Primary outcomes (receipt of Flu and Tdap vaccines) are binary and our main explanatory variable will be an indicator for study arm. We will employ intent-to-treat analyses using generalized linear mixed models (GLMMs) with practice random effects, an approach recommended for group-randomized RCTs in which the goal is to estimate the causal effects of interventions on individuals, adjusted for clustering within groups. This method performs well in situations where the number of observations per cluster is large and for unequal cluster sizes. Models will assume a binomial distribution and a log link function in order to compare vaccination rates between study arms in terms of risk ratios. We will adjust for all practice-level variables included in the randomization balancing criterion, as well as patient-level race/ethnicity (and prior year vaccination status for the flu analysis). Hypothesis tests will be two-sided with alpha = 0.025, reflecting a 2-fold Bonferroni correction for the co-primary endpoints of Flu and Tdap vaccination status, ensuring a familywise type I error rate of 0.05. Analyses will be performed using SAS v. 9.4 (SAS Institute Inc., Cary, NC).

Power Analysis: We assume national vaccine rates for flu (49%) and Tdap (54%). Adjusting for clustering of patients in practices, and assuming an intraclass correlation (ICC) of 1% (consistent with previous work), this sample size provides >80% power to detect an overall increase of 6.3 percentage point increase in vaccination rates between the QI intervention and control arms. This assumes a chi-squared test (a simplification of the planned mixed model analysis described above), a test-level alpha of 0.025, and a sample size of 5,000 pregnant women organized into 16 practices per study arm.

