#### 4. STUDY DESIGN & PROCEDURES (AIM/PHASE 2 ONLY)

##### **Brief Overview of Aim/Phase 2:**

Using a clustered RCT (randomizing practices), we will allocate half of the practices within each health system to the VAX-MOM intervention and the other half to standard of care. We will measure the impact of the intervention on vaccination rates (primary outcomes) and missed opportunities and process metrics (secondary outcomes) (see Table 4). Finally, if VAX-MOM is successful, we will provide the control practices the intervention during Year 3.

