##### **Design and Procedural Details of Aim/Phase 2:** (also see Figure 2 for Timeline)

###### **Step 1) Deliver VAX-MOM training/intervention to randomized practices:**

###### Randomization Details:

Practices will be the unit of randomization. We will assign practices using a covariate constrained randomization strategy as follows: First, we will use data from Aim #1 to obtain key factors that we expect to affect the primary outcomes. We will perform constrained randomization to allocate practices within each health system to intervention/control arms and ensure each arm has similar baseline flu and Tdap vaccination rates, percent of patients covered by Medicaid, number of OB providers, and number of patients. Specifically, we will use these variables to construct and evaluate a balance criterion, which is the sum of the squared difference between standardized group means on these variables. We will generate randomization separately by health system. We will generate all possible combinations of eligible practices in 2 arms (using a SAS macro), and define an acceptable set of randomizations that result in balanced variables (generally the lowest 10% on the balance criterion). From this set of randomizations, we will select one set at random, and then randomly assign each practice to intervention vs control group.

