## **6. INCLUSION/EXCLUSION CRITERIA & RECRUITMENT METHODS**

### All Participating Sites (Intervention & Control)

During aim/phase 1 of the study, health systems ([REDACTED]) within each state were chosen because a) their size allowed for an ample sampling of patients and practitioners (i.e., large subject pool) and b) they allowed for a broad spectrum of geographic and socio-economic diversity (e.g., privately and publicly insured, ethnic multiplicity, rural and urban locations, etc.). Prior to the start of the project, [REDACTED] contacted leadership within each health system, and letters of support were obtained (see attached Letters of Support for each system).

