### Intervention Sites

As described in the “Randomization” subsection of the “Study Design & Procedures” portion of the protocol, study sites from the larger pool were selected to be part of the “intervention group” using specific constrained randomization procedures within each health system (see section 4 of protocol for more details). All remaining sites were allocated to the “control group.”

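### Practices are randomised separately within four health systems, but the primary models contain no health-system term

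*Combined protocol and SAP*

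**What the plan says.** **Design.** The overview in section 4 plans to "allocate half of the practices within each health system to the VAX-MOM intervention", with the rest to standard of care. Randomization Details adds: "We will generate randomization separately by health system". Section 6 (Intervention Sites) confirms that sites were selected "using specific constrained randomization procedures within each health system". Within each system, the allocation is constrained so that the arms have "similar baseline flu and Tdap vaccination rates, percent of patients covered by Medicaid, number of OB providers, and number of patients".

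**Analysis.** Section 17 specifies "generalized linear mixed models (GLMMs) with practice random effects" for the two co-primary outcomes, and "Models will assume a binomial distribution and a log link function". On covariates it says: "We will adjust for all practice-level variables included in the randomization balancing criterion, as well as patient-level race/ethnicity". The flu model also adjusts for vaccination in the prior year. Tests are two-sided at 0.025 for each outcome. Section 17 has no health-system or state term, fixed or random.

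**The concern.** Section 17 adjusts for every practice-level variable that constrained the allocation but leaves out the stratum within which the allocation was made. A random intercept for practice alone treats practices as exchangeable across systems, which the randomisation did not do. Because the arms are balanced within systems, a difference between systems hardly affects the treatment estimate. It does enter the residual between-practice variance, so the reported standard error can be larger than the true spread of the estimate.

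Residual system differences are plausible:

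- Section 6 says of the chosen systems that "they allowed for a broad spectrum of geographic and socio-economic diversity".
- Public insurance in the four blocks of Table 6 is 55, 45, 1 and 75%.
- Each system's own report builder produces the outcome data, and manual chart review replaces a final report that is late (section 4, EHR data extraction).
- The Aim 1 rates come from births in summer 2018 to summer 2019, and the outcomes from 2021-2022. Aim 1 rates cannot carry a system-level change in practice or data capture that arose in between.

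At stake are the calibration of the standard error in both co-primary tests and some power. The validity of the tests is not in question. If the plan stays silent, adding the stratum after outcomes are seen would be a discretionary change to the primary analysis.

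**Working it through.** **1. The plan's power figure.** Inputs from section 17: rates 49% and 54%, increase 6.3 points, ICC 0.01, alpha 0.025, and 5,000 women in 16 practices, read as per arm. Cluster size is 5,000/16 = 312.5. The design effect is 1 + 311.5 × 0.01 = 4.115, and the effective n is 5,000/4.115 = 1,215 per arm. Power is 80.8% for flu and 81.6% for Tdap, so the stated figure reproduces. It does not depend on a system term.

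**2. The mechanism, without covariates.** Take 37 practices in blocks of 6, 16, 7 and 8 (Table 6), equal sizes of 10,000/37 = 270.3 women and a 49% rate. Assume that half of the between-practice variance lies between systems.

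- Between-practice variance: 0.01 × 0.49 × 0.51 = 0.00250, split into 0.00125 between and 0.00125 within systems.
- Sampling variance of a practice rate: 0.2499/270.3 = 0.00092.
- True SD of the arm difference: √[(0.00125 + 0.00092) × 4/37] = 0.0153.
- Share of the system variance that enters the residual when the term is left out: (37/36) × (1 − 405/1,369) = 0.724, where 405 = 6² + 16² + 7² + 8².
- Reported SE without the term: √[(0.00217 + 0.724 × 0.00125) × 4/37] = 0.0182.

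Simulation (8,000 replicates, least squares on practice rates) gave a true SD of 0.0155 and a mean SE of 0.0181 without the term. The test level was 1.2% without the term and 2.6% with it. At a share of 0 it was 2.5% either way. This is an upper guide, because the planned covariates are left out.

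**3. The planned model form.** The simulation used a binomial log-link GLMM with a practice random intercept, fitted by restricted pseudo-likelihood, with 4,000 replicates per cell. It used 36 practices with the Table 6 deliveries and providers, leaving out the practice with 0 deliveries. The four blocks were taken as the systems. Allocation was drawn from the best 10% on the balance criterion, with arm and the five balancing variables in the model.

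Assumptions: total ICC 1%; a share q of it between systems; correlation r of the Aim 1 rate with the practice effect; percent Medicaid equal to the block value plus noise of SD 12. Patient-level covariates were not simulated.

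Power (%) at 6.3 points, without → with the term:

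| q | Flu, r=0.5 | Flu, r=0.7 | Flu, r=0 | Flu, 32 practices, r=0.5 | Tdap, r=0.5 |
|---|---|---|---|---|---|
| 0 | 78.6→77.0 | 85.9→84.0 | 71.7→69.2 | 76.4→73.9 | 79.1→76.6 |
| 0.1 | 80.7→79.5 | 87.3→86.5 | 73.9→73.4 | 79.1→77.4 | 80.7→79.4 |
| 0.25 | 83.7→84.5 | 88.8→88.9 | 78.1→79.7 | 82.6→82.8 | 83.5→84.0 |
| 0.5 | 89.2→92.0 | 92.8→93.9 | 84.4→88.6 | 89.0→92.2 | 89.9→93.0 |

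If percent Medicaid carries half of the system effect (r=0.5), the results are 83.7→83.2 at q=0.25 and 91.1→92.0 at q=0.5. Only the differences matter. The absolute levels reflect the unequal practice sizes and a t reference, and do not test the plan's power claim.

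**4. Standard errors.** Reported over empirical SE without the term is 0.99-1.05 for q up to 0.25 and 1.02-1.06 at q=0.5. With the term it is 0.96-1.01. At q=0.5, r=0.5 the empirical SD of the log risk ratio is 0.0321 without and 0.0318 with the term, and the reported SE is 0.0336 and 0.0312. The ratios are 1.05 and 0.98.

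**5. A system shift at follow-up only.** An assumed SD across systems was added to the 1% ICC (q=0.1, r=0.5 / 0.7):

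- SD 0: 81.0→80.1 / 87.5→86.2
- SD 2 points: 78.3→79.1 / 84.5→85.5
- SD 3 points: 73.4→78.1 / 82.7→86.7
- SD 5 points (an upper extreme): 66.9→79.0 / 74.1→86.6

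Without the term, the SE ratio is 1.00-1.01, 1.01-1.03, 1.06-1.07 and 1.13-1.14 in turn.

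**6. A repeat.** A separate simulation with the Table 6 sizes, constrained allocation and five practice covariates gave about -2 points at q=0, roughly no change for q from 0.1 to 0.5, and +4 with a 3-point follow-up shift. SE ratios without the term rose from 1.00 to 1.06-1.09, against 0.99-1.02 with it.

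**The case against.** The case for leaving the model alone is serious. The test as planned is valid, and the true spread of the estimate is almost the same either way. At shares of 0 and 0.1 the term loses power in every cell, and consistent gains need about half of the practice variance to remain between systems. Race/ethnicity, which differs sharply across the Table 6 blocks, and prior-year flu vaccination are in the plan but not in the simulation. They point to a lower share.

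Calibration is not one-sided either: with the term the SE ratio falls as low as 0.96. With degrees of freedom equal to practices minus parameters, the test level was 2.4-3.3% with the term and 1.8-2.9% without it (nominal 2.5%, Monte Carlo SE 0.25). The follow-up shift appears nowhere in the documents. At 49% an ICC of 1% is a practice SD of about 5 points, so a 3-point shift adds 9/25 = 36% to the planned variance and a 5-point shift doubles it. Section 14 also provides for checking a small percentage of records.

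All of this limits the size of the point, and no power gain can be promised. It does not remove the mismatch between a stratified randomisation and an analysis that ignores the strata. The level question is a reason to name a small-sample method. In three cells run with Kenward-Roger, the level with the term fell from 2.5-3.2% to 2.2-3.0%, while power still rose (89.3→91.8, 76.2→77.5 and 73.9→78.9).

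**Conclusion.** The point holds as a modest one that should be corrected. Health system is the randomisation stratum and is missing from both primary models; the sentence on balancing variables does not cover it. The consequence is a possibly over-wide standard error and a conservative test. In the planned model form the excess is at most about 6% without a follow-up shift, and about 6 to 9% with a 3-point shift. The effect of the term on power runs from a loss of about 2.5 points to a gain of about 4 within the plan's 1% ICC, and reaches +4 to +5 with a 3-point shift. Where the trial falls in that range depends on the residual between-system variance, which the documents do not give, and on reading the Table 6 blocks as the four systems. The case rests on matching the analysis to the design and settling the choice in advance. Confidence in the size is medium.

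**What to change.** In section 17, before outcome data are seen:

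- Add health system as a four-level fixed effect to the flu and Tdap primary models.
- Name the degrees-of-freedom method, for example Kenward-Roger.
- Report the model without the term as a sensitivity analysis, and name it as the fallback if the log-link model with the term does not converge.
- Keep the Aim 1 rates as the baseline covariates. The 2019-2020 rates may be used in a sensitivity analysis.

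This takes one or two sentences and no new data. Practice-level degrees of freedom fall from 29 to 26 with 36 practices (36 minus 7 parameters, then minus 3), or from 25 to 22 with 32. About 1.5 to 2.5 points of power are lost if systems do not differ. Three more terms may also make the log-link model harder to fit, hence the named fallback.
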